**Application Of Bisection Rule:**

*Step (1)* Difference between the date mentioned on the CRF and the randomization date will be calculated.

$$\text{Difference day} = \begin{cases} \text{Date of assessment} - \text{date of randomization}, & \text{Assessments prior to randomization} \\ \text{Date of assessment} - \text{date of randomization} + 1, & \text{Otherwise} \end{cases}$$

*Step (2)*

There are seven pre-assigned nominal (planned) visit days according to the protocol.

- Screening (i.e. V0),
- Baseline(Safety Baseline) ( Day 1) (i.e.V1)
- Week 2 (Efficacy Baseline) (Day 14)(i.e.V2)
- Week 6 ( Day 42) (i.e.V3)
- Week 10 (Day 70) (i.e.V4)
- Week 14 (Day 98) (i.e.V5)
- Week 18 (Day 126)(i.e.V6)We choose intervals as follows (Table 19):

**Table 19: Visit Schedule (Part I)**

Visit	Visit Description	Target day	Range	
Visit 0	Screening	Screening	-28	0
Visit 1	Week 0	7	1	11

Visit	Visit Description	Target day	Range	
Visit 2	Week 2 #	14	12	28
Visit 3	Week 6	42	29	56
Visit 4	Week 10	70	57	84
Visit 5	Week 14	98	85	112
Visit 6	Week 18	126	113	141
Visit Y*	Every 4 Months	X	142	$[X + ((X - \text{Target day of previous visit}) / 2)]$

\*: Subsequent visit in Part II

#: Baseline for efficacy endpoints

### Step (3)

When there are multiple assessments in a particular visit window, the following rules are applied to select one value representing the subject in summary statistics.

- When there are multiple assessments falling in a particular visit window then the one which is closest to the scheduled visit day will be chosen. For safety assessments like Laboratory and Vitals consider average of observations.
- The visit will be missing if no assessment was reported within the specified visit window around the scheduled visit day.
- If the difference between two duplicate records is more than or equal to 14 days, then the former duplicate record will be assigned to previous visit. The difference of 14 days is chosen because the difference between all the visits is 28 days. For safety assessments like Laboratory and Vitals consider average of observations.

The details of the different assessments ([Table 20](#) and [Table 21](#)) to be done at each visit during the trial as follows:

Table 20: Schedule of Assessment (Part I)

Assessment	Screening	Run-in		Blinded Treatment Period				
		Baseline (Within 28 Days of Screening) Week 0	Week 2 (± 3 Days)	Week 6 Month 1 (± 7 Days)	Week 10 Month 2 (± 7 Days)	Week 14 Month 3 (± 7 Days)	Week 18 Month 4 (± 7 Days)	EOS (Early Discontinuation)
Informed Consent	X							
Inclusion/ Exclusion	X							
Medical History	X							
Prior and Concomitant Medication	X	X	X	X	X	X	X	X
WHO Functional Class	X	X	X	X	X	X	X	X
6 Min Walk Test	X	X a	X a	X	X	X	X	X
Borg Dyspnea, Heart Rate and SpO 2	X		X	X	X	X	X	X
Vital Signs (SpO 2 via Pulse Oximetry)	X	X	X	X	X	X	X	X
Total Lung Capacity (TLC)	X b							
Spirometry Testing (and DLCO)	X c						X	X
Physical Examination	X d						X	X
Pregnancy Test	X						X	X
MetHgb	X		X	X				X

Assessment	Screening	Run-in		Blinded Treatment Period				
Hematology, Chemistry	X						X	X
NT-proBNP	X						X	
Eligibility for INOpulse (Average Daily Use ≥ 12 hr/day)			X h					
Randomization		X						
Right Heart Catheterization (RHC) (Subset of ~ 50 Subjects)		X					X	X i
Right Heart Catheterization (RHC) (all subjects not enrolled in subset)	X j							
Echocardiogram for central reading (subset of ~50 subjects)		X			X		X	X i
Echocardiogram for local Reading only (all subjects not enrolled in subset)		X						X i
Evaluation of Symptomatic Rebound pH		X k	X					
Patient Reported Outcome (SF-36)		X					X	X
AE's/SAE's/AESI's		X	X	X	X	X	X	X
Drug Dispensing for Run-in period		X l						
Drug Dispensing for Treatment period			X l	X l	X l	X l	X l	

Assessment	Screening	Run-in		Blinded Treatment Period				
Drug Device Usage a			X n	X n	X n	X n	X n	X n
INOpulse questionnaire							X m	X
Survival Assessment			X	X	X	X	X	X
Medical Resource Utilization	X	X	X	X	X	X	X	X
Lung Transplantation Listing Status	X	X	X	X	X	X	X	X

a: A Screening 6MWT may be obtained at baseline if the subject is known to have a 6MWD  $\geq 100$  meters and  $\leq 450$  meters. The average of two 6MWD at Week 2 after run-in will be used at the baseline.

b: Total lung capacity test to be done if not performed within 6 months of screening.

c: DLCO (Diffusing Capacity for Lungs Measured Using Carbon Monoxide) will be performed at Screening Only.

d: Height and Weight to be performed at Screening.

e: N/A-Footnote no longer applicable as of Amendment #3

f: Pregnancy test to be performed at the discretion of investigator.

g: N/A-Footnote no longer applicable as of Amendment #3.

h: Subjects will be required to demonstrate an average daily usage  $\geq 12$  hours (rounded to the nearest hour) with no more than 2 days of usage  $< 8$  hours per day of the INOpulse device during the initial 2 weeks of the study in order to be eligible to continue to the treatment phase.

i: RHC should be obtained at early discontinuation only for subjects participating in RHC substudies ECHO should be obtained for all subjects at early discontinuation regardless if they are participating in the ECHO substudy.

j: A RHC will be conducted at Screening for subjects who are not included in this subset who have not had a RHC within the previous 5 years that meet eligibility criteria and are otherwise eligible.

k: After randomization at Week 0 and at end of Run-in, Week 2, all subjects will remain in the hospital or clinic for 1 hour after starting study drug and for 1 hour after study drug is discontinued for observation for signs and symptoms of rebound PH. Vital signs, including heart rate, respiratory rate, blood pressure, and SpO2 will be recorded in the supine position every 15 minutes for 1 hour, and then again every 15 minutes for another hour after discontinuation of study drug. After the 1 hour observation period off study drug, if the subject's status is unchanged with respect to vital signs and symptoms and subject does not exhibit signs or symptoms of rebound PH, they will restart their blinded study drug treatment and be sent home.

l: One week of drug dispensed to site at Baseline and Week 2; all other drug dispensed to subject's home via home delivery.

m: At Week 18 or prior to study discontinuation.

n: Site personnel should review INOpulse use with the subjects during study visits to encourage use as close to 24 hours per day as possible. Reasons for device interruptions should also be reviewed with the subject.

Table 21: Schedule of Assessment (Part II)

Assessment	Open Label Long Term Extension Period						
	Week 0 If subject enters Part 2, Week 0 assessments are done at Week 18 of Part 1	Week 2 (± 3 Days)	Week 16 Month 4 (± 14 Days)	Week 32 Month 8 (± 14 Days)	Week 52 Month 12 (± 14 Days)	Every 4 Months Until EOS (± 14 Days)	EOS (Early Discontinuation)
Informed Consent	X 						
Inclusion/Exclusion	X 						
Review of Prior and Concomitant Medications		X	X	X	X	X	X
WHO Functional Class			X	X	X		
6 Min Walk Test			X	X	X		
Borg Dyspnea, Heart Rate and SpO2			X	X	X		
Vital Signs(SpO2 via Pulse Oximetry)			X	X	X	X	X
Telephone contact		X					
Pregnancy Test	X		X 	X 	X 	X 	X 
MetHgb	X				X	X 	X
Hematology, Chemistry					X	X 	X

Assessment	Open Label Long Term Extension Period						
	Week 0 If subject enters Part 2, Week 0 assessments are done at Week 18 of Part 1	Week 2 (± 3 Days)	Week 16 Month 4 (± 14 Days)	Week 32 Month 8 (± 14 Days)	Week 52 Month 12 (± 14 Days)	Every 4 Months Until EOS (± 14 Days)	EOS (Early Discontinuation)
INOpulse Compliance and Check for Interruptions	X		X	X	X	X	X
Evaluation for Symptomatic Rebound PH	X 		X	X	X		
AEs/SAEs/AESIs	X	X	X	X	X	X	X
Drug Dispensing	X 		X 	X 	X 	X 	
Drug/Device Usage			X 	X 	X 	X 	X 

1 Ensure the subject has agreed to participate in both parts of the PAH-004 study by checking and initializing Part 1 & Part 2 participation in the ICF

2 Subject must have completed 18 weeks of blinded treatment

3 N/A-Footnote no longer applicable as of Amendment #3.

4 Pregnancy testing to be performed at the discretion of the Investigator.

5 Hematology and chemistry labs and MetHgb will be performed on a yearly basis.

6 Assessment Symptomatic Rebound PH: all subjects will remain in the hospital or clinic under medical supervision for 1 hour after starting study drug and for 1 hour after study drug is discontinued for observation for signs and symptoms of rebound PH. Vital signs, including heart rate, respiratory rate, blood pressure, and SpO2 will be recorded in the supine position every 15 minutes for 1 hour, and then again every 15 minutes for another hour after discontinuation of study drug. After the 1 hour observation period off study drug, if the subject's status is unchanged with respect to vital signs and symptoms and subject does not exhibit signs or symptoms of rebound PH, they will restart their blinded study drug treatment and be sent home.

7 Open Label Drug dispensed by site at Week 0; all other drug dispensed to subject's home via home delivery every 4 weeks thereafter

8 Site personnel should review INOpulse use with the subjects during study visits to encourage use as close to 24 hours per day as possible. Reasons for device interruptions should also be reviewed with the subject.

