7.1.4. Safety Endpoints

The safety endpoints include:

1. Incidence and severity of adverse events (AEs)
2. Incidence of device malfunction and/or device failure leading to an AE
3. Incidence of rebound pulmonary hypertension (PH)
4. Clinically significant changes in:
 - a. Clinical laboratory tests
 - b. Pulmonary function tests
 - c. Vital signs

7.2. Part 2 Open Label Period:

7.2.1 Primary Endpoint:

1. The incidence of AEs and SAEs with long term therapy

7.2.2 Secondary Endpoint:

1. To evaluate the change in 6MWD in subjects who switch from placebo to active therapy at 4 months, 8 months and 12 months of therapy

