11.1.15. Evaluation for Symptomatic Rebound Pulmonary Hypertension

In Part 1, after randomization at Week 0 and at end of Run-in, Week 2, all subjects will remain in the hospital or clinic under medical supervision for 1 hour after starting study drug and for 1 hour after study drug is discontinued for observation for signs and symptoms of rebound PH (see [Section 15.1.5](#)). Vital signs, including heart rate, respiratory rate, blood pressure, and SpO₂ will be recorded in the supine position every 15 minutes for 1 hour, and then again every 15 minutes for another hour after discontinuation of study drug.

At Week 0, INOpulse device should be set at 15 mcg/kg IBW/hr. At Week 2 the evaluation will be performed with the INOpulse device reset to 75 mcg/kg IBW/hr

In the opinion of the Investigator, subjects who develop clinically significant signs and/or symptoms consistent with rebound PH (e.g., systemic hypotension, change in heart rate, new onset syncope, or decreased systemic oxygenation) temporally associated with acute withdrawal, and including those associated with device malfunction or failure, will be discontinued from study treatment and not replaced (see [Section 10](#)).

In Part 2 evaluation should be performed at Week 0, Week 16 and Week 32 and Week 52.

During Part 2 if the subject develops clinically significant rebound PH, the subject may continue on open label therapy if it is considered in the opinion of the investigator to be in the subject's best interest.

The final diagnosis of rebound PH will be adjudicated by an ICEC. The DMC will review the data for subjects enrolled in the study and evaluated for rebound PH (including the ICEC adjudication) and make a decision whether or not to continue evaluation for rebound PH and/or to determine additional steps required in order to maintain subject safety.

After the 1 hour observation period off study drug, if the subject's status is unchanged with respect to vital signs and symptoms and subject does not exhibit signs or symptoms of rebound PH, they will restart their blinded study drug treatment and be sent home.

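### The SAP's averaging rule for vital signs does not exclude the rebound-test readings, so read literally the Week 0 safety baseline is 80–100% post-dose

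*SAP*

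**What the plan says.** **Averaging rule.** SAP 5.2, Step (3), says that when several assessments fall in one window "the following rules are applied to select one value representing the subject in summary statistics". In general the value nearest the planned day is taken. Laboratory tests and vital signs are treated differently: "For safety assessments like Laboratory and Vitals consider average of observations". The instruction appears twice, with no exception for rebound-test, post-dose or unscheduled readings.

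**Rebound test.** Under Protocol 11.1.15, repeated in footnote k of SAP Table 20, every subject at Week 0 and Week 2 is observed for 1 hour on study drug and 1 hour after it is stopped. The readings "will be recorded in the supine position every 15 minutes for 1 hour, and then again every 15 minutes for another hour" once the drug is off; they cover SpO2, blood pressure, and heart and respiratory rates. Both documents call these readings vital signs.

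**Safety baseline.** Step (2) of the SAP's bisection rule lists "Baseline(Safety Baseline) ( Day 1) (i.e.V1". The corresponding row of Table 19 reads "Visit 1 Week 0 7 1 11": target day 7, window days 1 to 11. SAP 6.4 defines the efficacy and SF-36 baselines and says nothing on safety.

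**Endpoint.** Protocol 7.1.4 lists "Clinically significant changes in" laboratory tests, pulmonary function tests and vital signs. SAP 7.7 plans laboratory summaries by arm. It specifies no vital-sign analysis, no table of the rebound series, and no worst-value, shift or threshold table.

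**The concern.** A safety baseline should describe the subject before treatment. Here study drug starts at the Week 0 visit, after randomization, and the baseline window opens on that same day. If every vital-sign value in the window is averaged, the baseline is mainly an average of readings taken during and just after first exposure.

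The rebound test is meant to show a short-lived change on withdrawal. Averaging on-drug and off-drug readings into one number hides that contrast in the Week 0 and Week 2 summaries.

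A third problem comes from the same rule. Part II Week 0 assessments, including a rebound test on open-label iNO, are done at the Part I Week 18 visit. SAP Table 19, the safety window table, has no row for Part II Week 0, so those readings fall in the Part I Week 18 window. For placebo subjects, active-drug readings could enter a blinded-period value.

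At stake are the descriptive vital-sign data for a listed safety endpoint, and any change from baseline computed from them.

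**Working it through.** The plan states no figure to reproduce. The check is a count of scheduled readings followed by simple means.

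**1. Readings per rebound test** (Protocol 11.1.15). Every 15 minutes for 1 hour is 60/15 = 4. Four on drug and four off drug make 8.

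**2. Routine readings at Week 0** (Protocol 11 and 11.1.7). There is one set of heart rate, respiratory rate and blood pressure. SpO2 is taken on room air and on prescribed oxygen, so two readings. These are assumed to be pre-dose; the order within the visit is not stated.

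**3. Day numbering** (SAP bisection rule, Step 1). For "Assessments prior to randomization" the day is the plain date difference; otherwise 1 is added. A same-day reading taken before randomization is therefore Day 0 if the rule is applied by clock time, and Table 19 places Day 0 in Visit 0 (−28 to 0). Applied by date only, it is Day 1 and stays in Visit 1.

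**4. Post-dose share of the Week 0 safety baseline.**

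| Case | Routine | Rebound | Post-dose share |
|---|---|---|---|
| Heart rate, respiratory rate, blood pressure | 1 | 8 | 8/9 = 89% |
| SpO2 | 2 | 8 | 8/10 = 80% |
| Pre-randomization set mapped to Day 0 | 0 | 8 | 8/8 = 100% |

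If each hour also has a time-zero reading, the series has 10 readings and the shares are 10/11 = 91%, 10/12 = 83% and 100%. Temperature is not among the rebound measurements and is unaffected.

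**5. Flattening of a short change** (assumed values, for scale only). The shift in the mean is the fall × k/n, where k of n readings are low.
- Systolic pressure, fall of 30 mmHg, n = 9: k = 1 gives 3.3, k = 2 gives 6.7, k = 4 gives 13.3 mmHg.
- SpO2, fall of 8 points, n = 10: k = 1 gives 0.8, k = 4 gives 3.2 points.

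The same counts apply at Week 2, where the rebound series falls in the window of days 12 to 28.

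**6. Week 18.** SAP Table 18 sets Part II Week 0 at Day 126, inside the Table 19 Week 18 window of 113 to 141. With one blinded routine set and 8 open-label readings, up to 8/9 = 89% of heart rate, respiratory rate and blood pressure readings in that mean could be open-label.

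**7. Laboratory tests** (assumed multiples of the upper limit of normal). Hematology and chemistry are scheduled at Screening and Week 18 or early discontinuation (Protocol 11.1.11), so none contributes to a Week 0 baseline. An abnormal value with a normal repeat, (3.5 + 1.0)/2 = 2.25, is diluted. Two abnormal values, (3.5 + 3.2)/2 = 3.35, stay abnormal.

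**8. Target-day conflict.** The other upper limits in Table 19 are midpoints of adjacent target days, for example (14 + 42)/2 = 28. The Week 0 limit of 11 fits target day 7, since (7 + 14)/2 = 10.5. It does not fit the Day 1 given in Step (2), since (1 + 14)/2 = 7.5.

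**The case against.** **Pooling is not stated.** The schedule lists vital signs and the rebound evaluation as separate assessments, described in separate protocol sections. Step (3) can be read as meant for repeat or off-schedule visits. This stands as a limit: a shared dataset is the literal reading, not a stated fact. It does not remove the point, because no text excludes the rebound readings and the choice is left to whoever programs the dataset.

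**Rebound detection is separate.** A reader might infer that averaging would hide cases of rebound pulmonary hypertension. The documents do not support that. The investigator identifies rebound, it is queried as an adverse event of special interest, the independent clinical events committee adjudicates it, and the data monitoring committee reviews it (Protocol 11.1.15, 11.1.17.1, 15.7). Step (3) governs summary statistics only.

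**Laboratory dilution is narrow.** A reader might infer that repeated abnormal results are averaged away. Two abnormal values generally average to an abnormal value, and results that qualify as adverse events are recorded as such (Protocol 15.4.1).

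**Thresholds.** The 90 mmHg systolic figure is a screening exclusion, and the 7% methemoglobin figure describes Phase 2 results. Neither is a safety cut-off for this trial, so neither measures the harm.

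**Mixed dose settings.** It is also tempting to say that the Week 2 mean mixes readings at the 15 and 75 mcg/kg IBW/hr settings. The documents give the 15 setting for the Week 2 walk test and the 75 setting for the rebound test, but not the device state for the routine Week 2 vital signs.

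**Baseline harm is conditional.** SAP 7.7 specifies no change-from-baseline analysis of vital signs. This stands: the effect depends on how clinically significant change is derived, which is left undefined.

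**Conclusion.** The point holds for vital signs. Followed as written, Step (3) gives a Week 0 safety baseline for heart rate, respiratory rate, blood pressure and SpO2 in which 80–100% of readings are post-dose. It merges on-drug and post-withdrawal readings in the Week 0 and Week 2 summaries, and it can bring open-label readings into the Part I Week 18 mean.

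This rests on three assumptions: the rebound readings share a dataset with the visit vital signs, the routine Week 0 set is taken before dosing, and there are four readings per hour. The first is decisive. If the series is held apart, the problem disappears, but the SAP would need to say so.

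The incidence of rebound pulmonary hypertension and of adverse events is not shown to be affected, and the laboratory effect is confined to an abnormal value followed by a normal unscheduled repeat. The SAP should be corrected, but the primary and secondary efficacy analyses are not touched.

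**What to change.** In SAP 5.2 and 6.4:

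1. Define the safety baseline as the last value before first dose; for laboratory tests this is the Screening value. The post-dose share of the Week 0 vital-sign baseline then falls from 80–100% to 0%.
2. Reconcile the Week 0 target day: Day 1 in Step (2), day 7 in Table 19.
3. Exclude rebound-test readings and all open-label readings from Part I visit values.

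In SAP 7.7:

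4. Tabulate the rebound series by arm and time point, as change from the last on-drug reading to the worst post-withdrawal reading.
5. For any abnormality or clinically-significant-change table, use all values, including repeats, in place of window means.

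The cost is SAP wording and one extra table from data already collected, with no change to visits or treatment. The downside is that tables built on all values will show more isolated outliers.

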**Table 3: Clinical Worsening Event**

Criteria #	Description
1	Death (all-cause mortality)
2	Atrial septostomy
3	Hospitalization due to worsening of PAH (adjudicated)
4	Start of new specific PAH treatment (endothelin receptor antagonists [ERAs], phosphodiesterase type-5 [PDE-5] inhibitors or prostanoids), an increase in the dose of an ERA or PDE-5, increase in the dose or frequency of an inhaled prostanoids, or an increase in the dose of an intravenous or subcutaneous prostanoids by >10%.
5	Decrease of >15% from baseline or >30% compared with the last study related measurement in 6MWD should be confirmed by a repeat measurement performed at least 14 days later.
6	Worsening of WHO Functional Class (e.g., from Class II to Class III or IV, OR Class III to Class IV); and should be confirmed by a repeat assessment at least 14 days later.

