**Table 4: Time Clinical Worsening Event Derivation**

Variables	Module	Source of Data	Derivation	Comments (to be removed later)
All-cause mortality	End of Therapy Status SAE	CRF	One-One mapping	Standard binary field
Atrial septostomy	End of Therapy Status	CRF	One-One mapping	Standard Binary field
Hospitalization due to worsening of PAH (adjudicated)	Adjudication Module	Non CRF	One-One mapping	Standard Field
New PAH treatment	PAH specific therapies	CRF	One-One mapping	Refer to new PAH Therapy Module
Decrease of >15% from baseline or >30% compared with the last study related measurement in 6MWD should be confirmed by a repeat measurement performed at least 14 days later	6 minute walk test	CRF	
1) Decrease of >15% from Baseline
 
Or
 
2) Greater than 30% compared with baseline
 
And
 
3) should be confirmed by repeat
	
Points (1) and (2) are simple derivations ;
 
Point (3) is linked to visit window mapping, so be careful.

Variables	Module	Source of Data	Derivation	Comments (to be removed later)
			measurement performed at least 14 days	
Worsening of WHO Functional Class (e.g., from Class II to Class III or IV, OR Class III to Class IV); and should be confirmed by a repeat assessment at least 14 days later	WHO functional class assessment done at every visit, choose only post baseline	CRF	(1) Class II to class III (2) Class III to class IV (3) Confirmation by repeat assessment at least 14 days later	Points (1) and (2) are simple derivations ;  Point (3) is linked to visit window mapping, so be careful.

2. Change in World Health Organization (WHO) Functional Class (Table 5 and Table 6) from baseline to 18 weeks

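### The SAP's 14-day rule for multiple records in one window always sends the earlier record to a farther Part 1 visit, and the Week 18 safety window has no cut at the first open-label dose; the practical reach is small.

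*SAP*

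**What the plan says.** SAP Section 5.2 gives two sets of visit windows. Tables 17 and 18 hold the protocol ranges, and the text after them assigns these to all efficacy analysis. A bisection mapping for safety follows, with wider windows in Table 19 and the rules for multiple records in Step (3).

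The first bullet of Step (3) says that, of several records in a window, "the one which is closest to the scheduled visit day will be chosen", with laboratory and vital-sign values averaged instead. The third bullet sets a further condition: "difference between two duplicate records is more than or equal to 14 days, then the former duplicate record will be assigned to previous visit". As its reason it states that "The difference of 14 days is chosen because the difference between all the visits is 28 days", and it repeats the averaging exception.

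Table 19 sets Week 18 at days 113 to 141 around a target of day 126. It also labels its Week 2 row "Baseline for efficacy endpoints". Table 21 places the Part 2 Week 0 assessments at the Part 1 Week 18 visit.

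**The concern.** A bisection window already places each record with its nearest target. A rule that then moves a record one visit back can only be sensible if the record is nearer the earlier visit, or if that visit would otherwise be empty. The third bullet checks neither. It also competes with the first bullet and no precedence is stated, so two programmers could build different datasets from the same SAP.

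The second issue is the end of the Week 18 window. Open-label iNO nominally starts on day 126, but records up to day 141 still map to Week 18. For a placebo subject, such a record reflects active drug. At stake is whether by-visit summaries of the blinded period contain only blinded data from the visit they name.

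**Working it through.** **Inputs.**
- Table 19 (target; window): Visit 1 (7; 1–11), Week 2 (14; 12–28), Week 6 (42; 29–56), Week 10 (70; 57–84), Week 14 (98; 85–112), Week 18 (126; 113–141).
- Table 17: targets 1, 14, 42, 70, 98, 126; ranges 11–17, 35–49, 63–77, 90–105 and 118–133 for Weeks 2 to 18.
- Table 18: targets 126, 140, 238, 350.

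**1. The SAP's own figure of 28 days.** The Part 1 gaps are 14 − 1 = 13, then 42 − 14 = 28, and 28 for each later gap. With Table 19's Visit 1 target of 7, the first gap is 7. The Part 2 gaps are 140 − 126 = 14, 238 − 140 = 98 and 350 − 238 = 112. The figure is reproduced only between Week 2 and Week 18.

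**2. Windows.** The midpoints (14 + 42)/2 = 28, (42 + 70)/2 = 56, (70 + 98)/2 = 84 and (98 + 126)/2 = 112 are the boundaries in Table 19. The Week 18 upper limit of 141 is not a midpoint: (126 + 140)/2 = 133 and (126 + 238)/2 = 182.

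**3. Which records move, and how far.** In a window from lo to hi, the earlier record must lie between lo and hi − 14. With w = hi − lo, the number of integer day pairs at least 14 days apart is (w − 13)(w − 12)/2.

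| Window | w | Earlier record, days | Days to own target | Days to previous target | Pairs | Moved farther | Earlier record in Table 17 range |
|---|---|---|---|---|---|---|---|
| Week 2 | 16 | 12–14 | 0–2 | 5–7 | 6 | 6 | 6 |
| Week 6 | 27 | 29–42 | 0–13 | 15–28 | 105 | 105 | 36 |
| Week 10 | 27 | 57–70 | 0–13 | 15–28 | 105 | 105 | 36 |
| Week 14 | 27 | 85–98 | 0–13 | 15–28 | 105 | 105 | 45 |
| Week 18 | 28 | 113–127 | 0–13 | 15–29 | 120 | 120 | 55 |
| Total | | | | | 441 | 441 | 178 |

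The extra distance is 2 to 28 days. Visit 1 (w = 10) is too narrow to trigger the rule. Two examples, each exactly 14 days apart:
- Days 42 and 56: the on-target Week 6 record goes to Week 2.
- Days 126 and 140: the on-target Week 18 record goes to Week 14, and day 140 stands for Week 18.

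**4. Efficacy windows (Table 17).** The same formula gives 0 pairs at Week 2 (w = 6), 1 each at Weeks 6 and 10 (w = 14), and 3 each at Weeks 14 and 18 (w = 15). The total is 8. The Week 18 pairs are 118/132, 118/133 and 119/133. All 8 move to a farther target.

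**5. How often a second record triggers the rule.** Assume the first record is uniform over the permitted days, and the second uniform over the remaining days of the Table 19 window. For a first record on day a, the share is (hi − a − 13)/(hi − a) where positive.
- Weeks 6 and 10: (8/21 + 7/20 + 6/19 + 5/18 + 4/17 + 3/16 + 2/15 + 1/14)/15 = 1.952/15 = 13.0%.
- Week 14: the printed range 90–105 adds 9/22, giving 2.361/16 = 14.8%; a strict ±7 days gives 13.0%.
- Week 18: the printed range 118–133 adds a further 10/23, giving 2.796/16 = 17.5%; a strict ±7 days gives 2.361/15 = 15.7%.

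The shares are therefore about 13–15% at Weeks 6 to 14 and 16–17.5% at Week 18, given that a second record exists in the same Table 19 window.

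**6. The first bullet alone.** Of the 55 Week 18 pairs whose earlier record is in the Table 17 range, 51 keep that record, 2 tie (118/134, 119/133) and 2 choose the later one (118/132, 118/133). All 40 pairs of an in-range Week 18 record with a later record on days 137–141 keep the Week 18 record.

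**The case against.** The case against is mainly about reach, and most of it stands.

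- **Scope.** Efficacy is sent to Tables 17 and 18, where day 56 is not in Week 6 and day 140 is not in Week 18. Table 19 and Step (3) come under the safety heading. This is not quite conclusive, because Table 19 marks the efficacy baseline and Step (3) is the SAP's only rule for multiple records.
- **Averaging.** Laboratory and vital-sign values are exempt from selection, so few scheduled assessments remain for the rule to act on.
- **Open-label records.** The Part 2 Week 2 contact is a telephone call for medications and adverse events (protocol Section 11). No walk, WHO class or Borg score is scheduled again until Part 2 Week 16. An open-label value in the Week 18 window would need an unscheduled assessment or an early Part 2 discontinuation.
- **Drafting.** The third bullet can be read as a specific exception to the first. That would settle precedence, but the exception would still go the wrong way.

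A reader might infer wider damage, which the documents do not support:

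- *6MWD baseline.* It is fixed separately as the mean of the two Week 2 walks (SAP Sections 4.1 and 7.3.1). Nothing says that a relabelled walk enters that mean.
- *TTCW.* A decline in walk distance "should be confirmed by a repeat measurement performed at least 14 days later", the same interval that triggers the rule, and Table 4 remarks that "Point (3) is linked to visit window mapping, so be careful". But TTCW runs on dates from randomization (SAP Section 7.4.1), Step (3) selects values for summary statistics, and the Table 4 remark is in a comments column marked for removal.
- *Pulmonary function.* Spirometry is scheduled only at Screening and at Week 18 or early discontinuation, so no second record is planned in a post-baseline window.

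**Conclusion.** The rule is wrong wherever it can fire in the Table 19 windows for Weeks 2 to 18, and its stated reason does not hold across the schedule. The consequence is minor. The primary 6MWD analysis is barely exposed, with three edge pairs at Week 18 even if Step (3) is carried over to Table 17.

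Two limits apply to the result. The record moved is not always an on-time one: in 65 of the 120 Week 18 pairs it falls outside the Table 17 range. The finding also does not extend to the open-ended Part 2 window: taking X = 238 and a previous target of 126, an earlier record on days 142–181 would move to a nearer visit.

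The trigger shares rest on the uniform assumptions and on a second record whose probability the documents do not give, so no count of affected subjects follows. The missing open-label cut at Week 18 is a separate gap. It matters for averaged values as well, because averaging would mix blinded and open-label results.

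**What to change.** Delete the third bullet of Step (3), so that the closest-record rule governs every assessment that is not averaged. The averaging exception is already in the first bullet, so nothing is lost. Add one sentence that ends every Part 1 window at the first open-label dose, for averaged values too; the closest-record rule alone would not keep open-label values out of an average. The two tied pairs show that a short tie-break is also useful.

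The cost is one deletion and one or two sentences in the SAP before unblinding. Data collection, sample size and the primary model do not change.
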